5. RESEARCH OBJECTIVES

- 1) To compare plasma levels, biopsy mRNA (using low density expression arrays) and protein (using either Luminex or Western blotting) levels of the following parameters between IBD patients treated with Frondanol and those treated with placebo at baseline and after six months of treatment:
 - a) Cytokines: TNF α , IL1 β , IL6, IL17A, IL21, IL22, IL23, IFN γ , IFN α , as well as vascular endothelial growth factor (VEGF-A), MIP-1, MIP-2;
 - b) Markers of inflammation: Myeloperoxidase, calprotectin, S100A12, β 2-microglobulin, amyloid A (A-SAA), intercellular adhesion molecule 1 (ICAM-1), vascular cell adhesion molecule 1 (VCAM-1), MIP-2 α (CXCL2), MCP-1 (CCL2). Leukotriene B4 (LTB4), 5-hydroxyeicosatetraenoic acid (5-HETE) and prostaglandin E2 (PGE2) will be measured by specific ELISA assays.
- 2) To compare the following routine clinical parameters between IBD patients treated with Frondanol and those treated with placebo at baseline and after six months of treatment:
 - a) Patient symptoms;
 - b) Blood: Complete blood count (CBC), erythrocyte sedimentation rate (ESR), C-reactive protein (CRP), albumin;
 - c) Stool: Fecal calprotectin level;
 - d) Endoscopic and histologic features.
- 3) To compare in-vitro concentration-dependent responses to Frondanol and placebo on inflamed organoids by measurement of cytokines and other inflammatory markers, in particular 5-HETE, LTB4 and PGE2.

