6.2 Study setting

Patients will be seen in-person at the Gastroenterology Department of any of the study centres that will participate in patient recruitment (Mediclinic City Hospital, Mediclinic Parkview Hospital and Rashid hospital) by one of the coninvestigator consultant gastroenterologists at screening and randomization (T0), at a follow-up visit at 3 months (T1), and at a second follow-up visit at 6 months (T2). Routine blood tests as well as an extra sample for research

RJ

Version 3.2. Effective Date: 04 December 2021

purposes will be obtained at these timepoints. Colonoscopies will be performed as part of the routine clinical practice and these include acquisition of routine biopsies, typically 10-15 from each patient. A few additional biopsies (2-4) will be needed for our studies, to be snap frozen and analyzed in MBRU research laboratory facilities. IRB approval for these additional biopsies and serological testing is being sought from both Mediclinic City Hospital's REC, MBRU-IRB and DHA-REC. It is hoped that the routine colonoscopies can be scheduled prior to starting the study treatment and 6 months later.

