6.13 Subject Identification

All patient data and specimen will be de-identified and coded with the unique study number of the patient. The code linking the study number with the patient will be accessed by the study coordinator only and maintained at MBRU in a database and will not be provided to the PI or her research team. Patient data will be collected using protocol-specific case report forms (CRFs), which will be used to create electronic CRFs (e-CRFs). Clinical records for all patients, including CRFs, will be retained by the PI in a secure storage facility for ten years after the completion of the study. Paper data will be stored in a locked

RJ

Version 3.2. Effective Date: 04 December 2021

cabinet and electronic data will be stored on a password-protected computer in the custody of the PI. The data linking patient identifying information and their de-identified data will be in the custody of the study coordinator who will be unblinded. All patients will complete the following study visits: Screening (medical history, physical examination, vital signs and standard of care tests including blood and stool tests), baseline endoscopy (day 1 of treatment, date to be agreed between the gastroenterologist and patient), 3 months (routine monitoring with standard of care tests including blood and stool tests), 6 months (second endoscopy and standard of care tests including blood and stool tests).

 -
RJ

Version 3.2. Effective Date: 04 December 2021

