6.14 Study schedule

Table 1: Variables to be collected from participants

Method of data collection	Variables
Questionnaires	Mayo Score, IBDQ
Medical record	Symptoms
Blood samples	Routine blood tests as well as an extra sample (10 mL) for research purposes will be obtained at T0 (start of study), T1 (3 months) and T2 (6 months).
Stool samples	Routine stool sample will be collected for measurement of fetal calprotectin levels at the recruiting hospital at T0, T1 and T2.
Tissue samples	Colonoscopies will be performed as part of the routine clinical practice and these include acquisition of routine biopsies, typically 10-15 from each patient. A few additional biopsies (2-4) will be collected for our studies during routine colonoscopies when these are performed, then they will be snap frozen and analyzed in MBRU research laboratory facilities.

Table 2: Schedule of Activities

Variable	Visit # 1 (T0)	Visit # 2 (T1 – 3months)	Visit # 3 (T2 – 6 months)
Questionnaires	Mayo Score, IBDQ	Mayo Score, IBDQ	Mayo Score, IBDQ
Medical record	Symptoms	Symptoms	Symptoms
Blood samples	Routine blood tests as well as an extra sample (10 mL) will be obtained, stored and analyzed in MBRU research laboratory facilities.	Routine blood tests as well as an extra sample (10 mL) will be obtained, stored and analyzed in MBRU research laboratory facilities.	Routine blood tests as well as an extra sample (10 mL) will be obtained, stored and analyzed in MBRU research laboratory facilities.
Stool sample	Routine stool sample will be collected for measurement of fetal calprotectin levels at MCH	Routine stool sample will be collected for measurement of fetal calprotectin levels at MCH	Routine stool sample will be collected for measurement of fetal calprotectin levels at MCH
Tissue samples	If colonoscopy is performed for routine clinical practice at the start of the study, a few additional biopsies (2-4) will be collected for our studies, snap frozen and analyzed in	No tissue samples collected	If colonoscopy is performed for routine clinical practice at the end of the study, a few additional biopsies (2-4) will be collected for our studies, snap frozen and analyzed in

RJ

Version 3.2. Effective Date: 04 December 2021

	MBRU research laboratory facilities.	MBRU research laboratory facilities.
--	--------------------------------------	--------------------------------------

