7. SAFETY CONSIDERATIONS

The recommended dose on the marketed neutraceutical product of Frondanol is 1000 mg twice daily. Over the past 25 years more than 3 million 1000 mg capsules have been consumed in the human market, with no reported side effects. Hence, we based the dosing for our study on the marketed recommended dose, as we do not anticipate any side effects. We will be excluding patients with allergy to seafood or marine products to avoid the risk of allergic reactions.

Colonoscopies performed in this study are considered part of routine care and not for research purposes. The overall expected rate of serious complications (bleeding or perforation) from routine colonoscopies is 2-3 per 1000 procedures (Lee and Salzman, 2020). The only additional procedure that is done for the research is to take several additional biopsies after all routine biopsies are taken. The expected increase in risk from taking these several additional biopsies is considered to be very small and likely insignificant. The consent form will state that the “increased risk of taking additional biopsies, for the purposes of this research, after all routine biopsies are taken is considered to be very small.”

In the unlikely event that side effects occur, patients will be requested to immediately inform the study coordinator/research nurse, PI or consultant gastroenterologist. A direct phone number will be given to patients so that they are able to call the study coordinator or assigned nurse in case of any adverse events. Depending on the severity of the event, the participant will be instructed whether to report to the Gastroenterology unit at the study site or to head to the emergency department of one of the hospitals covered by the trial's liability insurance, for further investigation and possible treatment.

Additional risks to the study subjects would be embarrassment or discomfort in answering items on questionnaires to be completed. Participants will be instructed not to answer any questions that they feel uncomfortable with.

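### The schedule makes six-month tissue depend on a routine colonoscopy, in conflict with Section 6.13; if scoping follows disease course, the tissue, endoscopic and histologic comparisons may no longer compare the randomised arms

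*Combined protocol and SAP*

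**What the plan says.** Tissue collection is conditional at both ends of the study. Table 2 in Section 6.14 says for T2: "If colonoscopy is performed for routine clinical practice at the end of the study, a few additional biopsies (2-4) will be collected". For T0 it says: "If colonoscopy is performed for routine clinical practice at the start of the study, a few additional biopsies (2-4) will be collected". Table 1 says the extra biopsies "will be collected for our studies during routine colonoscopies when these are performed". No tissue is taken at T1 (3 months).

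Two other sections agree. Section 6.2 says of timing: "It is hoped that the routine colonoscopies can be scheduled prior to starting the study treatment and 6 months later". Section 7 says: "Colonoscopies performed in this study are considered part of routine care and not for research purposes".

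Section 6.13 reads differently. It begins "All patients will complete the following study visits" and then lists a baseline endoscopy and, at 6 months, a second endoscopy.

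The outcomes affected are in Section 5: "biopsy mRNA (using low density expression arrays") and tissue protein in objective 1, and endoscopic and histologic features in objective 2d. Section 8.2 assesses efficacy in participants with complete data. It adds an intention-to-treat analysis that carries the last observation forward (LOCF) for patients who drop out. It has no rule for a patient who stays in the study but is not scoped.

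**The concern.** Under Tables 1 and 2, whether a patient supplies T2 tissue is settled by routine care after randomisation. If patients with returning symptoms are scoped more often than patients who feel well, and Frondanol changes symptoms, then treatment helps to decide who is in the tissue comparison. Scoped Frondanol patients and scoped placebo patients would then differ for reasons other than the effect of treatment on tissue. Blinding does not prevent this: it stops decisions based on known allocation, not decisions based on symptoms that treatment has altered.

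At stake is the most direct evidence on the trial's stated aim, bowel inflammation.

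**Working it through.** **1. The texts side by side.** Section 6.14 (Tables 1 and 2), Section 6.2 and Section 7 make colonoscopy a matter of routine care, with timing hoped for. Section 6.13 gives every patient a second endoscopy. If Section 6.13 governs, there is no planned selection. If the schedule governs, there may be. The documents give no indication for the six-month colonoscopy, no expected share scoped, and no link to symptoms or calprotectin.

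**2. What Section 8.2 does with an unscoped patient.** The complete-data analysis leaves the patient out of the tissue comparison. LOCF is specified for dropouts. If it were applied here, the absence of T1 tissue means that it could carry forward only T0 tissue, which is itself conditional. A true 0.5 SD change would shrink to 0.5 × the share scoped: 0.40, 0.25 or 0.15 SD at 80%, 50% or 30% scoped.

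**3. Precision.** Section 8.1 gives no power calculation to reproduce; only 100 patients (50 per arm) is stated. With two-sided alpha 0.05 (sidedness assumed) and 80% power, the detectable difference is (1.96 + 0.84) × √(2/n). The shares are assumptions.

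| Share with T2 tissue | n per arm | Detectable difference | Power for 0.5 SD |
|---|---|---|---|
| 100% | 50 | 0.56 SD | 70% |
| 80% | 40 | 0.63 SD | 61% |
| 50% | 25 | 0.79 SD | 42% |
| 30% | 15 | 1.02 SD | 28% |

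A repeated-measures analysis needs tissue at both T0 and T2. If the two are independent at 80% each, 50 × 0.8 × 0.8 = 32 per arm have a pair; at 50% each, 12.5.

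**4. Bias in a flare model.** Assumptions, none from the documents: flare in 30% on placebo and in 15% or 20% on Frondanol; tissue marker 1.5 SD higher in a flare; T2 colonoscopy in 90% of flaring patients (s1) and in 20% or 60% of the others (s0). The flare share among scoped patients is p·s1 / [p·s1 + (1 − p)·s0].

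| s0 | Flare rate, Frondanol | Flare share among scoped, placebo / Frondanol | Difference among scoped | True difference | Excess |
|---|---|---|---|---|---|
| 20% | 15% | 0.659 / 0.443 | 0.324 SD | 0.225 SD | 44% |
| 20% | 20% | 0.659 / 0.529 | 0.194 SD | 0.150 SD | 29% |
| 60% | 15% | 0.391 / 0.209 | 0.273 SD | 0.225 SD | 21% |
| 60% | 20% | 0.391 / 0.273 | 0.178 SD | 0.150 SD | 19% |

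The expected number scoped runs from 50 × 0.305 = 15.25 to 50 × 0.69 = 34.5 per arm. With SD 1 within flare state, the standard error of the difference is 0.30-0.42. The excess of 0.03-0.10 SD is therefore 0.09-0.24 standard errors.

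**5. Bias in a continuous model.** Simulation with 2 million patients per arm. Assumptions: 30-50% of controls scoped; odds of colonoscopy multiplied by 1 to 4 per SD of disease activity; activity-tissue correlation 0.5-0.8.

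- Scoping unrelated to activity: a true 0.5 SD benefit is estimated as 0.50. Precision is lost, but there is no bias.
- Odds ratio 2 to 4, with treatment improving activity and tissue by 0.5 SD each: the estimate is 0.478 to 0.394 SD, a loss of 1 − 0.478/0.5 = 4% to 1 − 0.394/0.5 = 21%.
- Odds ratio 2 to 4, with symptoms improved by 0.5 SD and tissue unchanged: scoped Frondanol patients look 0.02-0.11 SD more inflamed. With a symptom effect of 0.5-0.8 SD, correlation 0.6 and a log-odds slope of 1-2, this becomes 0.05-0.19 SD.
- No effect on either: bias 0.00, even under strong selection.

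**6. Can it be repaired?** In the symptom-only case just given (correlation 0.6), with scoping dependent on recorded symptoms alone, regression imputation on symptoms within arm and weighting by the true scoping probability each brought the bias to within about 0.01 SD of zero.

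**The case against.** Section 6.13 schedules a second endoscopy for all patients, and Section 6.2 describes timing by calendar. On that reading most patients may be scoped at six months whatever their course, and the loss is of precision only. No passage ties colonoscopy to symptoms. The trial is a self-described pilot, and limiting extra biopsies to routine colonoscopies is a deliberate choice. The bias is small beside the sampling error in the flare model. All of this stands, and it rules out four stronger conclusions that a reader might draw:

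- That T2 tissue exists only for patients scoped in routine care. Section 6.13 says otherwise, so the documents show a conflict.
- That the tissue comparison has definitely lost randomisation. This requires scoping to depend on a course that treatment changes, which the documents neither state nor exclude.
- That the effect will look too large, or change sign. The direction depends on the assumed model. The flare cases keep the sign, and in the symptom-only case the true tissue effect is zero, so there is no sign to reverse.
- That no imputation could help. Imputation and weighting both work if scoping depends on recorded data, and neither is assured if it does not.

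The objection does not remove the point. Section 6.13 stands against three sections that treat colonoscopy as routine care, and Section 8.2 has no plan for unscoped patients under either reading.

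**Conclusion.** The point holds in conditional form. The documents conflict on whether every patient has a second endoscopy. If collection stays conditional and scoping follows a disease course that treatment affects, the tissue, endoscopic and histologic comparisons among scoped patients are open to selection after randomisation. The illustrations run from 19-44% overstatement to about 4-21% understatement of a true difference, and up to 0.19 SD of spurious harm where only symptoms improve. Every input to these figures is an assumption. The bias is nil if scoping is purely by calendar or if the product is inert. The loss of precision needs no such assumption about why patients are scoped, only that some are not. This should be settled before the analysis plan is final; it does not undermine the plasma, stool or symptom outcomes, which are scheduled for all patients.

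**What to change.** 1. State which text governs, and bring Sections 6.2, 6.13, 6.14 and 7 into line.
2. If collection stays conditional, add one case report form field, completed before the randomisation number is issued: is a routine colonoscopy at about 6 months already planned (yes/no)?
3. Record the indication for each T2 colonoscopy, planned or symptom-driven, when it is ordered. Report the number scoped by arm and indication.
4. In Section 8.2, for tissue, endoscopic and histologic outcomes, replace the complete-data and LOCF approach with two analyses side by side. The first is a by-arm comparison in patients marked as planned at T0, stating how many of them were in fact scoped. The second covers all randomised patients, weighted or imputed from Mayo score, CRP and fecal calprotectin at T0 to T2, with symptom-driven colonoscopies flagged.

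The planned subset is defined before randomisation, so the comparison is protected to the extent that planned colonoscopies are done; patients who feel well may still skip them. Its size is unknown and may be small, and weights from a few dozen scoped patients may be unstable. That is why neither analysis should stand alone, and why the tissue estimates should be described as imprecise. The cost is one new field, recording the indication, a few sentences in Section 8.2 and a little more analysis. No extra colonoscopy is needed.

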6.15 Definition of End of Study

The study ends after six months of treatment with either Frondanol or placebo.

7. SAFETY CONSIDERATIONS

The recommended dose on the marketed neutraceutical product of Frondanol is 1000 mg twice daily. Over the past 25 years more than 3 million 1000 mg capsules have been consumed in the human market, with no reported side effects. Hence, we based the dosing for our study on the marketed recommended dose, as we do not anticipate any side effects. We will be excluding patients with allergy to seafood or marine products to avoid the risk of allergic reactions.

Colonoscopies performed in this study are considered part of routine care and not for research purposes. The overall expected rate of serious complications (bleeding or perforation) from routine colonoscopies is 2-3 per 1000 procedures (Lee and Salzman, 2020). The only additional procedure that is done for the research is to take several additional biopsies after all routine biopsies are taken. The expected increase in risk from taking these several additional biopsies is considered to be very small and likely insignificant. The consent form will state that the “increased risk of taking additional biopsies, for the purposes of this research, after all routine biopsies are taken is considered to be very small.”

In the unlikely event that side effects occur, patients will be requested to immediately inform the study coordinator/research nurse, PI or consultant gastroenterologist. A direct phone number will be given to patients so that they are able to call the study coordinator or assigned nurse in case of any adverse events. Depending on the severity of the event, the participant will be instructed whether to report to the Gastroenterology unit at the study site or to head to the emergency department of one of the hospitals covered by the trial's liability insurance, for further investigation and possible treatment.

Additional risks to the study subjects would be embarrassment or discomfort in answering items on questionnaires to be completed. Participants will be instructed not to answer any questions that they feel uncomfortable with.

8. STUDY OUTCOME EVALUATIONS/STATISTICAL ANALYSIS

8.1 Sample size/Power calculation

All eligible IBD patients visiting the Gastroenterology Department of any of the study centres that will participate in patient recruitment (Mediclinic City Hospital, Mediclinic Parkview Hospital and Rashid hospital) under the care of

RJ

Version 3.2. Effective Date: 04 December 2021

any of the coninvestigator consultant gastroenterologists during the period of recruitment (12 months from the start date of the study – to be decided following ethical approval) will be offered to take part in the study.

Patients will be randomised (1:1) to receive Frondanol (one 1000 mg capsule twice daily) or placebo (in a similar capsule) as an adjunct to their standard therapy using a randomization number sequence generator. This will be conducted by the study statistician using the Microsoft Excel random number generator and will only be shared with the study coordinator.

All patients and investigators, excluding the study coordinator, will be blinded to treatment allocation.

8.2 Statistical methods

All statistical analyses will be carried out using SPSS Software (Armonk, New York, USA). Potential confounders such as age and sex will be controlled for during the analysis phase. A per-protocol analysis including only participants who have a full data set will be used to assess the efficacy of Frondanol treatment in lowering inflammatory markers. An intention-to-treat analysis will also be conducted including patients who drop out before the study ends, for whom we will use last observation carried forward (LOCF) i.e. we will impute the last observed data for all subsequent (missing) observation points. For quantitative data, within-group and between-group comparisons will be analyzed using the General linear Repeated Model (MANOVA), which would allow for adjustment of potential confounders such as age and sex. Data will be plotted as mean \pm SEM and p values <0.05 will be considered statistically significant.

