Over the past 25 years, it is estimated that more than three million Frondanol capsules have been consumed on the human market with no reported side effects. An even larger amount has been consumed on the veterinary market without a single reported incident. If proven beneficial, Frondanol, will be a useful supplement in treating the underlying chronic gut inflammation in IBD patients, increasing the likelihood of patients remaining in remission and potentially providing an effective, natural and safe treatment for treatment naive patients in the future.

The proposed study is a pilot, double-blinded, placebo-controlled trial of Frondanol in patients with IBD (Crohn's disease or ulcerative colitis) who are currently in remission and are on standard therapy. One hundred patients will be randomized (1:1) to receive Frondanol or placebo as an adjunct to their standard therapy for the period of six months. Blood and tissue samples from colon biopsies obtained during routine visits and endoscopies at baseline and six months later will be collected. The levels of inflammatory markers such as myeloperoxidase, tumor necrosis factor (TNF)- α , interleukin (IL)1 β , IL6, IL17A, IL22, interferon gamma (IFN- γ) and several other inflammatory markers will be compared between patients treated with Frondanol and those treated with placebo, and the findings will be correlated with clinical and histological parameters. In addition, we plan to develop a stem cell-derived gut organoid model to investigate the mechanism of action of Frondanol.

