6.5 Eligibility criteria

- **Inclusion criteria:**

A confirmed clinical diagnosis of IBD of any duration, age 18 years or older, with mild to moderate disease and on standard therapy. The diagnostic criteria for IBD include the presence of chronic diarrhoea for more than four weeks, and evidence of active inflammation on endoscopy and chronic changes on biopsy. Patients with stable mild to moderate IBD will be eligible for the study. Stable IBD is defined as having stable symptoms over a period of several weeks, diagnostic evaluation has been completed and the patient has been on consistent medication. Mild to moderate IBD is indicated by a Partial Mayo score (Mayo Clinic Score/Disease Activity Index for Colitis) of between 1-6, and a total of Mayo score of 1-10 (Pabla and Schwartz, 2020). For patients with Crohn's disease, only those with Crohn's colitis will be included (patients with small bowel disease are eligible to enter the trial as long as they also have large bowel inflammation).

- **Exclusion criteria:**

Pregnancy, breastfeeding, allergy to seafood or marine products, severe medical illness such as uncontrolled diabetes ($\text{HbA1C}>10$), significant or unstable cardiovascular or pulmonary disease, impaired renal function ($\text{Cr}>2.0\text{mg/dL}$), current or recent (<1 year) malignancy, or other significant medical illness that in the view of the investigators may impair participation in the study. Patients with severe IBD (defined by a Partial Mayo score of 7-9 and a total Mayo score of 11-12 (Pabla and Schwartz, 2020), with active symptoms) will not be eligible to participate in the study.

Reference:

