6.11 Withdrawal from the study

The following paragraph is included in the consent form regarding withdrawal from the study:

“You are at liberty to withdraw from the research study at any stage, without prejudice. Should any new information become available that may affect your willingness in participation, you will be informed in a timely manner. However, the principal investigator or designee may take you out of the study at any time with or without your agreement. This may happen for example if it is in your best medical interest to stop your participation, or if the study is canceled. If you wish to withdraw from the study, any collected data will be safely stored for a minimum of three years following the completion of the study then discarded in a confidential manner that does not risk identifying your personal information.”

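### Section 8.2 assesses marker efficacy only in patients with full data and backs it with an intention-to-treat analysis using LOCF; both can distort the treatment effect

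*Combined protocol and SAP*

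**What the plan says.** Section 8.2 plans two analyses. The first is labelled per-protocol: an "analysis including only participants who have a full data set will be used to assess the efficacy of Frondanol treatment in lowering inflammatory markers". It has no adherence criterion, and what counts as a full data set is not defined. The second follows: "An intention-to-treat analysis will also be conducted including patients who drop out before the study ends". For these patients, "we will impute the last observed data for all subsequent (missing) observation points". Neither analysis is called primary. Quantitative data go into the SPSS repeated-measures general linear model (MANOVA), with adjustment for age and sex. There is no other missing-data rule and no sensitivity analysis.

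Other sections bear on who will have data:

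- **Visits.** Under Table 2 in section 6.14, blood and stool are taken at T0, T1 (3 months) and T2 (6 months). Tissue is taken at T0 and T2 only, and only if a routine colonoscopy takes place. Section 6.2 says: "It is hoped that the routine colonoscopies can be scheduled prior to starting the study treatment and 6 months later". Section 6.13, by contrast, lists both endoscopies among the visits that every patient completes.
- **Exit.** Under section 6.10, data collection ends at withdrawal. The consent text in section 6.11 lets the investigator remove a patient: "This may happen for example if it is in your best medical interest to stop your participation".
- **Hoped-for benefit.** Section 3 describes it as "increasing the likelihood of patients remaining in remission".
- **Entry.** Section 6.5 requires stable disease: "Stable IBD is defined as having stable symptoms over a period of several weeks".
- **Sample size.** Section 8.1 gives no effect size, SD or drop-out rate.

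**The concern.** Selecting on completeness happens after randomisation, so the groups compared need not be the groups randomised. If exit follows disease course and Frondanol works, a single exit rule applied to both arms can remove more placebo patients than active ones. Completers then no longer give a like-for-like comparison.

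The intention-to-treat analysis should be the safeguard, but LOCF has its own problems. A patient who leaves before T1 is given the baseline value at 6 months, which records no change. That dilutes a real effect. It can also create a false difference if drop-out differs by arm while markers drift in both.

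Two gaps add to this. LOCF is stated for drop-outs, so no rule clearly covers a patient who stays but misses a sample. The repeated-measures GLM needs complete rows, so that patient can fall out of both analyses of that endpoint. And if full data set means every marker item, a missing routine biopsy also removes the patient from the blood and stool comparisons.

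**Working it through.** **Inputs.** From the documents: 50 per arm, 1:1 allocation, visits T0, T1 and T2, significance at 0.05 (taken as two-sided). Everything else is assumed: SD 1 at each visit, equal correlation r of 0.5 to 0.7 between visits, and all drop-out rates and effects. The contrast is the between-arm difference in T2-T0 change. The plan has no figure of its own to reproduce.

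**(a) LOCF with equal random drop-out p, true effect 0.50 SD.** Completers stay at 0.50.

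- All leave before T1: 0.50 x (1-p). For p = 10%, 20%, 30% this gives 0.45, 0.40, 0.35 SD.
- All leave after T1, half the effect present there: 0.50 x (1-p) + 0.25 x p = 0.475, 0.45, 0.425 SD.
- Full effect already present at T1: no dilution.

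**(b) LOCF with no true effect.** Simulation of 40,000 trials per setting, 50 per arm, common linear change in both arms, t-test on change. Ranges cover r = 0.5 and 0.7.

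| Random drop-out before T1 | Type I error, common change 0.25 SD | Type I error, common change 0.5 SD |
|---|---|---|
| 15% vs 25% | 5.2-5.7% | 5.8-6.7% |
| 10% vs 30% | 6.0-6.6% | 8.7-10.7% |

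If everyone leaves after T1, the range is 5.0-6.4%. Completers, and LOCF with equal drop-out, stay at about 5%.

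**(c) The same exit rule in both arms.** T2 is missing if the marker rose by more than 0.8 SD from T0 to T1; true effect -0.50 SD. At r = 0.5 the T1-T0 change has SD 1 and the regression of T2-T0 change on it has slope 0.5, so the full-effect case can be done by hand (φ, Φ: standard normal density and distribution function):

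- Drop-out: placebo 1-Φ(0.8) = 21%; active 1-Φ(1.3) = 10%.
- Completers: placebo -0.5 x 0.2897/0.7881 = -0.184; active -0.5 - 0.5 x 0.1714/0.9032 = -0.595. Difference -0.411.
- LOCF: placebo 0.7881 x (-0.184) + 0.2897 = 0.145; active 0.9032 x (-0.595) + (0.0968 x (-0.5) + 0.1714) = -0.414. Difference -0.559.

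Simulation with 3 million per arm agrees (-0.412 and -0.560) and extends this to r = 0.6 and 0.7:

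| Effect at T1 | Drop-out, placebo / active | Completers | LOCF | Likelihood model using T1 |
|---|---|---|---|---|
| Full | 15-21% / 5-10% | -0.41 to -0.43 | -0.55 to -0.56 | -0.50 |
| Half | 15-21% / 9-15% | -0.45 to -0.46 | -0.49 to -0.51 | -0.50 |

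If exit depends on the T1 level instead of the rise, completers give -0.50. With no true effect, a common rule gives 0 for every method.

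A stronger assumption is worsening-driven exit after T1 fixed at 10% placebo and 30% active, with no true effect and r = 0.6. Completers then give -0.12 SD with type I error 9.2%, LOCF gives +0.07 SD, and a missing-at-random method gives 0.00.

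**(d) Tissue, which has no T1.** Under rule (c) with full effect at T1, completers give -0.41 to -0.43 on change, or -0.45 adjusted for baseline. LOCF from baseline gives -0.39 to -0.42. A mixed model does no better than baseline-adjusted completers, because no tissue value at T1 carries the information that drove exit.

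**(e) Every-item reading of full data set.** Three blood, three stool and two tissue items; each non-tissue item is present with probability a (0.95 or 0.98), each colonoscopy with probability b, all independent. Patients qualifying out of 100 = 100 x a^6 x b^2.

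| b | a = 0.95 | a = 0.98 |
|---|---|---|
| 1.0 (as in section 6.13) | 74 | 89 |
| 0.8 | 47 | 57 |
| 0.6 | 26.5 | 32 |

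Read per endpoint, plasma keeps 100 x a^3 = 86 to 94.

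**The case against.** The strongest reply is that the distortion is small where the assumptions are most natural. Blinding makes a common exit rule the natural case. The completer bias under (c) is then 0.04 to 0.09 SD, against a standard error of about 0.15 to 0.20 SD at 50 per arm. It runs against Frondanol. Nominal 95% intervals still cover the true effect in 93-95% of trials for completers and 94-95% for LOCF, and type I error stays near 5%. A clearly raised false-positive rate needs drop-out that differs markedly by arm. For LOCF it also needs a common drift, in patients chosen for stable disease. The documents supply neither. All of this stands, and it limits the severity.

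Other points stand in part:

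- The dilution in (a) is a bias only if the target is the effect had everyone stayed on treatment. The plan states no target, and the mixed model answers that question under missing at random.
- That the complete-data analysis leads is an inference from its order, its tie to efficacy and the word 'also'.
- A missed T1 sample removes a patient only if T1 enters the model. Section 5 compares baseline with six months, so this is open. A patient with no T2 visit might reasonably be treated as a drop-out.
- The every-item reading is the extreme one, and the counts of 27 to 57 rest on assumed colonoscopy rates.
- The evidence for disease-driven exit is general consent wording and a conditional statement of benefit.

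None of this supplies a better missing-data method. Blinding does not stop a real effect from changing who leaves.

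**Conclusion.** The concern holds and should be fixed. The analysis tied to marker efficacy does not keep the randomised groups intact, and the intention-to-treat analysis relies on LOCF. The two can err in opposite directions, as in (c) with full effect at T1, or only one may be wrong, as in (a). Neither their agreement nor their disagreement shows which to believe.

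Confidence is high that the method is inferior to an available one. The size in this trial is unknown, because no drop-out or colonoscopy rate is given. Under the assumed settings with a true effect of 0.50 SD, the error is about 0.04 to 0.09 SD for completers under a common exit rule and up to 0.15 SD for LOCF with 30% early random drop-out. Completers are unbiased under random missingness and in some other settings. Blinding, stable disease at entry and pilot status argue against a higher grade.

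**What to change.** In section 8.2:

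1. Name as primary an analysis of all randomised patients by assigned arm, endpoint by endpoint. Use a likelihood-based mixed model with baseline and every observed T1 and T2 value (SPSS MIXED), in place of LOCF and the repeated-measures GLM.
2. Keep the complete-data analysis as a sensitivity analysis, and define completeness separately for each endpoint.
3. For tissue, drop LOCF, label paired-biopsy results exploratory and selected, and report missingness by arm.
4. Limit any sensitivity analysis for data not missing at random to one or a few key endpoints named in advance.

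Separately, section 6.13 must be reconciled with section 6.2, section 7 and Table 2 on whether all patients have endoscopy. Section 6.10 should also make clear that data collected before withdrawal remain in the intention-to-treat analysis, if that is the intention.

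The cost is wording, a different SPSS procedure and slightly more analysis work, with no extra patients or visits. The downside is that the mixed model assumes data are missing at random, and it gains nothing for tissue.
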